8.2. Setting

[figure not shown]
This study will be conducted using data from four Nordic countries: Denmark, Finland, Norway, and Sweden (listed alphabetically) in each country, all live births and stillbirths are recorded in the birth registries (in all countries from gestational week 22 from July 2008 onwards; in Sweden, from gestational week 28 until July 2008). During those periods there were approximately 580,000 – 730,000 live births in each of Denmark, Finland, and Norway, and 800,000 in Sweden.¹⁶ The start of the study period in each country is selected to ensure availability of pregabalin and the candidate comparator on the market and availability of data on outpatient dispensings for at least 12 months before the end of the earliest identified pregnancy. For example, pregnancy ending at term with a live birth on 1 January 2005 in Denmark will have prescription history from 1 January 2004, thus covering the 9 months of gestation and 3 months preconception.

Population-based healthcare registries in Nordic countries are an optimal setting for examining safety of medicines in pregnancy. Their most important strengths are capture of all births and, in some cases, clinically relevant birth and postnatal outcomes; routine capture of dispensings of prescription medications to pregnant women; extensive information about maternal and offspring health outcomes; and exact linkage between the maternal and the offspring record. Thus, unlike studies based e.g., on data from TIS, there is no risk of bias by self-referral, recall, or access to health care. Dispensings of medicines represent a better proxy of actual drug intake than do issued prescriptions (primary compliance), reducing misclassification of the actual drug intake.

Study population

The study population consists of all pregnancies identified in the respective administrative registries from 1 January 2005 to 31 December 2015 in Denmark, Finland, and Norway and all pregnancies identified from 1 July 2006 to 31 December 2013 in Sweden, Figure 1 .

Figure 1. Study population flow diagram

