8.3. Variables

8.3.1. Exposures

For the purposes of timing of exposure, trimesters of pregnancy will be defined as follows:

- First trimester: from the first day of the last menstrual period (LMP)-90 days to LMP+97 days (both dates inclusive);
- Second trimester: from LMP+98 days to LMP+202 days (both dates inclusive);
- Third trimester: from LMP+203 days (inclusive) until pregnancy end date (not included).

Exposure during the first trimester

Pregabalin exposure during the first trimester will be defined as at least one maternal dispensing of pregabalin during the first trimester. Pregabalin monotherapy in the first trimester will be defined as first-trimester exposure to pregabalin and no first-trimester dispensing for any other AED.

Comparators:

Unexposed to pregabalin during the first trimester comparator is defined as pregnancies without a dispensing for pregabalin or any other AED, including lamotrigine or duloxetine, during the first trimester.

Lamotrigine exposure in the first trimester is defined by at least one dispensing of lamotrigine during the first trimester. Lamotrigine monotherapy in the first trimester will be defined as first-trimester exposure to lamotrigine and no first-trimester dispensing for any other AED.

Duloxetine exposure in the first trimester is defined by at least one dispensing of duloxetine during the first trimester. Duloxetine monotherapy in the first trimester will be defined as first-trimester exposure to duloxetine and no first-trimester dispensing for any AED.

Lamotrigine or duloxetine exposure in the first trimester is defined by at least one dispensing of lamotrigine or duloxetine or both during the first trimester. Lamotrigine or duloxetine monotherapy in the first trimester will be defined as first-trimester dispensing of lamotrigine or duloxetine or both and no first-trimester dispensing for any other AED.

For analyses that use lamotrigine as the comparator, pregnancies exposed to both pregabalin and lamotrigine in the first trimester will be excluded. For analyses that use duloxetine as the comparator, pregnancies exposed to both pregabalin and duloxetine in the first trimester will be excluded.

Exposure any time during pregnancy

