Pregabalin exposure any time during pregnancy is defined by at least one dispensing of pregabalin during any trimester. Pregabalin monotherapy any time during pregnancy will be defined as any-pregnancy exposure to pregabalin and no dispensing for any other AED during any trimester.

Comparators:

Unexposed to pregabalin during any trimester comparator is defined as pregnancies without dispensing for pregabalin or other AEDs including lamotrigine, or duloxetine during any trimester.

Lamotrigine exposure any time during pregnancy is defined by at least one dispensing of lamotrigine during any trimester. Lamotrigine monotherapy any time during pregnancy will be defined as any-pregnancy exposure to lamotrigine and no dispensing for any other AED during any trimester.

Duloxetine exposure any time during pregnancy is defined by at least one dispensing of duloxetine during any trimester. Duloxetine monotherapy any time during pregnancy will be defined as any-pregnancy exposure to duloxetine and no dispensing for any AED during any trimester.

Lamotrigine or duloxetine exposure any time during pregnancy defined by at least one dispensing of lamotrigine or duloxetine or both during any trimester. Lamotrigine or duloxetine monotherapy any time during pregnancy will be defined as any-pregnancy exposure to lamotrigine or duloxetine or both and no dispensing for any other AED during any trimester.

For analyses that use lamotrigine as the comparator pregnancies exposed to both pregabalin and lamotrigine in any trimester will be excluded. For analyses that use duloxetine as the comparator pregnancies exposed to both pregabalin and duloxetine in any trimester will be excluded.

In a sensitivity analysis, monotherapy with pregabalin, lamotrigine, and/or duloxetine will be defined by absence of other AED, selective serotonin reuptake inhibitors, or benzodiazepines.

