8.3.2.1. Primary Outcomes (Birth outcomes)

- Major congenital malformations, any and specific, according to the European Network of Congenital Anomaly Registers (EUROCAT) classification²⁰
- Stillbirth, as recorded in each country's birth registry
- Low birth weight (birth weight < 2500 g)
- Small for gestational age (SGA), defined, for singleton pregnancies, as a dichotomous variable (yes/no) of birth weight below 2 standard deviations (SDs) of sex- and gestational week specific distributions, using country-specific reference standard.^{19,21} SGA non-singleton gestations will be defined if appropriate reference standard can be defined/identified; otherwise set to missing.
- Preterm birth, defined as gestational age <37 weeks
- Low Apgar score at 5 minutes, defined as a dichotomous variable (score 0-6 vs. score 7-10)
- Microcephaly, defined as a dichotomous variable (yes/no) of head circumference at birth (cm) smaller than 2 SD of sex- and gestational week specific distribution, using country-specific reference standard

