- for the outcomes other than congenital malformations: maternal medication use each as a dichotomous variable, defined by at least one dispensing during any trimester (AEDs, antidepressants, hypnotics, antipsychotics, analgesics, antihypertensives, non-steroidal anti-inflammatory drugs, drugs for peptic ulcer/gastroesophageal reflux, folic acid, drugs for in-vitro fertilization, thyroid hormones, systemic corticosteroids, and antiinfectives for systemic use).

[figure not shown]
Full list of the study variables and their operational definitions are provided in [Annex 3](#).

Figure 2. Examples of follow up period for neurodevelopmental outcomes during the study period

[figure not shown]
1.

2.

3.

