8.4. Data sources

Data sources used to construct the analysis data set for this study are presented in Table 3. Within each country, records from all registries are linkable at the individual level by a unique national person identifier. For births recorded in the birth registries, a maternal unique identifier is a variable on the record of the offspring, enabling exact linkage between a given offspring and maternal history of medication dispensing or diagnoses before or during pregnancy.

Diagnosis in all countries are registered based on the ICD-10 coding system and accessed through registers as specified in Table 3. Similarly medications are classified according to the ATC coding system and accessed through prescription registers. The medical birth registers in the included countries furthermore contain similar information other relevant covariates (calendar year of delivery, maternal age at conception, parity; marital/cohabiting status; pregravid body mass index (BMI); smoking during pregnancy; single or multiple pregnancy; and child's sex.)

Validity of routine data in Nordic national registries has been found to be high in all countries.²²⁻³⁷ In Denmark, positive predictive value of diagnoses of cardiac malformations is 89%.³⁸ For drugs used chronically, there is also high level of agreement between general practitioner and dispensing records.³⁹ An agreement between dispensing records and drug use reported in the standard medical antenatal records included in the birth register was 69% for antiepileptics in Sweden.⁴⁰

Table 3. National registries in Denmark, Finland, Norway and Sweden and type of data available from each registry

Study variable/role	Type of data	Data source(s)	Coding system(s) used
Person identification (mothers and children)	Unique personal identifier for data linkage	Danish Civil Registration System ⁴¹ Danish Civil Registration System Finnish Medical Birth Register* National Registry of Norway Swedish Total Population Register ⁴²	N/A
Study population	Pregnancies ending in singleton/multiple live birth or stillbirth	Danish Medical Birth Registry Finnish Medical Birth Register* Medical Birth Registry of Norway Swedish Medical Birth Register Danish National Patient Registry ^{43,44}	A specific variable in each birth registry

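### Counting any dispensing up to delivery as exposure builds immortal time into stillbirth, preterm birth and low birth weight against the unexposed

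*Protocol*

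**What the plan says.** Section 8.3.1 of the protocol fixes the windows. The early one is "First trimester: from the first day of the last menstrual period (LMP)-90 days to LMP+97 days (both dates inclusive". The late one is "Third trimester: from LMP+203 days (inclusive) until pregnancy end date (not included". For all outcomes other than malformations the exposed group follows from these: "Pregabalin exposure any time during pregnancy is defined by at least one dispensing of pregabalin during any trimester". The reference group mirrors it: "Unexposed to pregabalin during any trimester comparator is defined as pregnancies without dispensing for pregabalin or other AEDs including lamotrigine, or duloxetine during any trimester".

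Section 8.3.2.1 has "Preterm birth, defined as gestational age <37 weeks" among the primary outcomes, with stillbirth and low birth weight. Sections 8.7.3 and 8.7.4 compare these outcomes by any-trimester exposure in log-binomial regression, so exposure is one fixed status per pregnancy. Section 8.2 gives the start of registration: "in all countries from gestational week 22 from July 2008 onwards; in Sweden, from gestational week 28 until July 2008".

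For the same outcomes, section 8.3.3 measures medication covariates over the same open window: "defined by at least one dispensing during any trimester (AEDs, antidepressants, hypnotics".

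The sensitivity analyses in section 8.7.6 cover second-trimester induced abortions and a stricter definition of monotherapy. None uses a landmark, a time-varying exposure or a different exposure window. Section 8.9 places study entry at the estimated conception date and treats selection from inclusion as a lesser concern. It concedes in general terms that dispensing may misstate the timing of intake, but does not discuss a window that ends with the outcome.

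**The concern.** The window closes when the pregnancy ends, so its length depends on the outcome. A pregnancy that ends at week 30 has ten weeks less in which to collect a first fill than one that ends at week 40. Women who would have started pregabalin late but delivered early, or had a stillbirth, fall into the unexposed group. Those counted as late starters have, by construction, reached their first fill without the event. Entry at conception with exposure assigned months later is the usual immortal-time structure.

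Low birth weight is touched through its dependence on gestational length. The medication covariates share the fault: a fill of an antihypertensive or a corticosteroid late in pregnancy may follow from exposure, from a complication or simply from a longer pregnancy, and it enters the propensity score.

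The bias runs towards no effect or apparent protection. In a safety study that is the falsely reassuring direction, on primary outcomes and in the comparison with the unexposed. A larger sample does not remove it.

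**Working it through.** **1. The plan's own precision figure.** The upper limit that can be ruled out is exp[(1.960 + 0.842) × SE], with SE = √[(1−p)/(n·p) × (1 + 1/119)]. With p = 0.03 and n = 1000 this gives 1.65844; section 8.5 states 1.65845. With p = 0.10 it gives 1.306; Table 5 states 1.3.

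**2. Late starters, from Table 4.**
- Pregabalin: first trimester 200+700+200+400 = 1500; any time 350+900+350+800 = 2400; late share 900/2400 = 37.5%.
- Lamotrigine: 6200 and 8300; 2100/8300 = 25.3%.
- Duloxetine: 1800 and 3200; 1400/3200 = 43.75%.

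**3. Which late fills matter.** Every cohort pregnancy has reached registration, week 22 or 154 days (week 28 for early Swedish stillbirths). Fills between LMP+98 and LMP+153 therefore create no immortal time. The share of intended late fills at LMP+154 or after depends on timing, which the protocol does not give:
- even over LMP+98 to +280: 126/182 = 69%, or 0.375 × 0.69 = 26% of the exposed;
- all in the second trimester (LMP+98 to +202): 48/104 = 46%, or 17%;
- front-loaded, exponential with mean 60 days: exp(−56/60) = 39%, or 15%.

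Under the even assumption, 21/182 = 11.5% of late first fills (about 104 of 900) fall at LMP+259 or later, where preterm birth is impossible.

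**4. Expected ratio under no effect.** I simulated gestational age at delivery and an independent intended first fill that counts only if it precedes delivery. The group ratio is (1 − w) + w × R, where w is the late share and R the late starters' risk relative to all pregnancies. Preterm births were set at 5 to 10% of deliveries. The distributions within preterm birth and over fill time are assumptions.

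| Outcome and assumption | R | Pregabalin vs unexposed (w = 0.375) |
|---|---|---|
| Preterm, 85% of it at 32–36 weeks, fills even to LMP+280 | 0.80 | 0.925 |
| Same, fills in second trimester only | 0.988 | 0.995 |
| Preterm, 70% of it at 34–36 weeks and the rest spread over 22–33, fills even to LMP+280 | 0.76 | 0.91 |
| Same, fills in second trimester only | 0.963 | 0.986 |
| Stillbirth (0.6%, spread over days 154–290), fills even to LMP+280 | 0.707 | 0.89 |
| Same, fills in second trimester only | 0.923 | 0.97 |

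Low birth weight was not simulated.

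**5. Active comparators, even filling to LMP+280.**
- Preterm (R = 0.80): lamotrigine 1 − 0.253 × 0.20 = 0.949, duloxetine 1 − 0.4375 × 0.20 = 0.9125. Pregabalin's 0.925 over these gives 0.97 and 1.01.
- Stillbirth (R = 0.707): lamotrigine 0.926, duloxetine 0.872. Pregabalin's 0.89 over these gives 0.96 and 1.02.

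**6. Size against precision, with 2400 exposed and 119:1.**
- Preterm at 10%: SE = 0.061 and the excludable ratio is 1.19. A ratio of 0.91 is a shift of 0.094, or 1.5 SE; 0.99 is a shift of 0.010, or 0.2 SE.
- Stillbirth at 0.6%: SE = 0.264. A ratio of 0.89 is a shift of 0.117, or 0.4 SE.

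**7. Pre-LMP days.** 90 of the 90 + 98 = 188 first-trimester days (48%) precede LMP. If v is the share of the exposed group truly exposed, observed RR = 1 + v(RR − 1). The protocol gives no v. As an assumed range only, an upper limit of 1.66 excludes true ratios above 1 + 0.66/0.9 = 1.73 (v = 0.9) to 1 + 0.66/0.5 = 2.32 (v = 0.5).

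**The case against.** Several counter-arguments stand. Not all of the 37.5% is affected, since fills before LMP+154 do no harm. The 37.5% itself is approximate: Table 4 holds rounded pilot estimates, Norway's column is copied from Denmark's, and the window behind the pilot's first trimester is not stated. For preterm birth the bias is close to nothing if late starters fill mainly in the second trimester. For stillbirth it sits well within random error. A reader might infer from the differing late shares that the active-comparator contrasts are biased as much as the unexposed one. They are not: the factors largely cancel, and against duloxetine the small remainder goes the other way. Section 8.1 already plans to read estimates across comparators.

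A reader might also take the 48% of pre-LMP days as the share of users not exposed in utero, and call the LMP−90 start an error. The documents do not support that. Days are not users; only women whose sole fill was before LMP matter, and their number is not given. Section 8.2 refers to three months of preconception history. A look-back of that kind can capture supply carried into pregnancy, and it keeps such women out of the unexposed group. Nor can the agreement figure in section 8.4, which "was 69% for antiepileptics in Sweden", be used for v. It compares dispensing records with drug use in antenatal records, says nothing about pre-LMP-only fills, and would leave the same disagreement under a narrower window.

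None of this removes the central point. The any-time window does end at delivery, the analysis treats exposure as fixed, and no planned analysis tests the consequence.

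**Conclusion.** The concern holds for stillbirth, preterm birth and low birth weight in the comparison with the unexposed. Followed as written, the plan biases these ratios downward: about 0.91 to 0.99 for preterm birth and 0.89 to 0.97 for stillbirth when the true ratio is 1. No figure is offered for low birth weight. These sizes rest on assumed fill timing and gestational-age distributions and on Table 4's approximate late share; the direction does not. For preterm birth the bias can exceed one standard error; for stillbirth it is small beside the imprecision. Contrasts with lamotrigine and duloxetine are little affected (about 0.96 to 1.02).

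The pre-LMP part of the first-trimester window is a defensible choice whose dilution is unknown. It warrants an added sensitivity analysis, not a correction.

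**What to change.** For stillbirth, preterm birth and low birth weight, classify pregabalin, comparator and unexposed status by dispensings up to LMP+153 only. For Swedish stillbirths registered from week 28 before July 2008 the cut-off could be LMP+195, or LMP+153 can be applied throughout. State that women first dispensed after the cut-off stay in the group they belong to at that date. Excluding them for a later fill would condition on the future and bring in a new selection. The alternative is a Cox model on gestational age from week 22 with time-varying exposure. Measure the section 8.3.3 medication covariates for these outcomes no later than the same cut-off.

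Separately, as sensitivity analyses, report women whose only fill was from LMP−90 to LMP−1 as their own row, and add a malformation analysis that requires a dispensing from LMP to LMP+97, with the pre-LMP-only women kept out of the unexposed group.

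Cost: the changes are to definitions and coding on the same registry data, and this version precedes the planned start of extraction. Some exposed pregnancies change group, some late exposure is counted as unexposed, and the stricter malformation analysis has fewer exposed. Further propensity-score sets are needed in each of the four countries (three for the malformation analysis if it is run with the abortion data) beyond the 16 listed in section 8.7.3.1.

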8.3.2. Outcomes

This study will describe use and assess safety of pregabalin use during pregnancy based on a series or birth and postnatal outcomes. For each outcome defined below, the population (denominator), period of pregnancy identification, and follow-up for outcome assessment are described in Table 2.

Table 2. Types of pregnancies included in analysis of each outcome for the primary analyses, secondary analyses, and sensitivity analyses

Outcome	Study population and period of pregnancy identification				Follow-up for outcome assessment
	Denmark	Finland	Norway	Sweden	

Table 2. Types of pregnancies included in analysis of each outcome for the primary analyses, secondary analyses, and sensitivity analyses

Outcome	Study population and period of pregnancy identification				Follow-up for outcome assessment
	Denmark	Finland	Norway	Sweden	
Primary analyses	Major congenital malformations (overall and specific)	Pregnancies ending in singleton/multiple live birth, stillbirth, 1Jan2005 - 31Dec2015 inclusive		Pregnancies ending in singleton/multiple live birth or stillbirth 1Jul2006-31Dec2013 inclusive	Prevalence at birth with outcomes identified at birth, and until the first birthday (inclusive) through 2016 in Denmark, Finland and Norway and through 2014 in Sweden
	Stillbirth	Pregnancies ending in singleton/multiple live birth, stillbirth, 1Jan2005 - 31Dec2015 inclusive		Pregnancies ending in singleton/multiple live birth or stillbirth 1Jul2006-31Dec2013 inclusive	Prevalence at birth
	Low birth weight	Pregnancies ending in singleton/multiple live birth, 1Jan2005 - 31Dec2015 inclusive		Pregnancies ending in singleton/multiple live birth 1Jul2006-31Dec2013 inclusive	Prevalence at birth
	SGA ¹⁹				
	Preterm birth				
Secondary analyses	Low Apgar score at 5 minutes				
	Microcephaly				
	Attention deficit hyperactivity disorder	Pregnancies ending in singleton/multiple live birth, 1Jan2005 - 31Dec2015 inclusive	Pregnancies ending in singleton/multiple live birth, 1Jan2008 - 31Dec2015 inclusive	Pregnancies ending in singleton/multiple live birth 1Jul2006-31Dec2013 inclusive	Minimum 1 year postnatally. Maximum available postnatally, 31Dec 2016 Denmark, Finland, Norway; 31Dec 2014 Sweden.
Sensitivity analyses	Autism spectrum disorders				
Sensitivity analyses	Learning disabilities (including mental retardation)				
Sensitivity analyses	Major congenital malformations (overall and specific) including malformations identified prenatally	Pregnancies ending in singleton/multiple live birth, stillbirth, 1Jan2005 - 31Dec2015 inclusive and pregnancies ending in therapeutic 2 nd trimester induced abortion, 1Jan2005-31Dec2015 inclusive (Denmark, Norway) 31Dec2012 (Finland)		None	Prevalence at birth with outcomes identified prenatally, at birth, and until the first birthday (inclusive) through 2016 in Denmark and Norway and 31Dec2016 in Finland

SGA, Small for gestational age.

* The Patient Registry of Norway, the source of data for the postnatal outcomes, has existed from 2008.

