All singleton and multiple gestations ending in live birth or stillbirth will be identified in each country's birth registry from 1 January 2005 to 31 December 2015 in Denmark, Finland, and Norway and pregnancies identified from 1 July 2006 to 31 December 2013 in Sweden. As all birth outcomes will have occurred as of the date of delivery, prevalence will be used as a measure of outcome occurrence.¹⁴ However, to allow for delayed reporting/diagnosis, all congenital malformations diagnosis recorded until one year of age will be included, according to the standard procedure used by the European Network of Congenital Anomaly Registers (EUROCAT)¹⁷ through the end of 2016 in Denmark, Finland and Norway and through the end of 2014 in Sweden. In addition, available information on pregnancies ending in 2nd trimester therapeutic induced abortions will be identified in Denmark, Finland and Norway.¹⁸ Information on pregnancies ending in 2nd trimester therapeutic induced abortions is not available from Sweden. It will be especially important to identify pregnancy terminations due to malformations of the nervous system, as nearly half of the pregnancies affected by nervous system malformations may be terminated.¹⁸

For the birth outcomes, stillbirth prevalences at birth will be described and compared among the live and still born infants. For the birth outcomes other than congenital malformations or stillbirth, prevalences at birth will be described and compared.

For the postnatal neurodevelopmental outcomes, live-born offspring of all pregabalin-exposed and the comparator pregnancies will be followed from the date of birth until the earliest record of a given outcome of interest, emigration (except Sweden and Norway, where emigration data are unavailable), death, or end of study (31 December 2014 in Sweden; 31 December 2016 in the other countries); for this analysis children in Norway born before 2008 will be excluded as the Patient Registry of Norway was launched in 2008. Thus, for the neurodevelopmental postnatal outcomes, live-born children will be followed up to a minimum of 1 year and a maximum of 10 years postnatally in Denmark, Finland, and Norway and up to a maximum 8.5 years postnatally in Sweden (Figure 2).

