8.5. Study size

Table 4 shows estimated number of total pregnancies ending in live or stillbirth and pregnancies with exposures and indications potentially relevant for analysis.

Table 4. Estimated numbers of pregnancies ending in live or still birth for potentially analysis-relevant categories

	Denmark (2005-2016)	Finland (2005-2014)	Norway* (2005-2016)	Sweden (2006-2013)
Pregnancies ending in live/still birth	730,000	580,000	650,000	800,000
Pregnancies with dispensation of				
Pregabalin, first trimester	200	700	200	400
Pregabalin, any time during pregnancy	350	900	350	800
Lamotrigine, first trimester	2000	900	2000	1300
Lamotrigine, any time during pregnancy	2700	1100	2700	1800
Duloxetine, first trimester	400	500	400	500
Duloxetine, any time during pregnancy	800	600	800	1000

*Pilot data not available; estimated based on pilot data from Denmark due to similar s population size.

The estimated numbers of pregnancies ending in live or still birth for potentially analysis-relevant categories for Norway were unavailable at the time of the protocol writing but are estimated in Table 4 by imputing data from Denmark, where the number of pregabalin users was the lowest, to provide the most conservative estimate. Based on this and on each country’s population size, conservatively estimated achievable size for this study will be more than 1000 pregnancies exposed to pregabalin during the first trimester.^{20,51} Table 5 shows the maximum upper limit of the 95% confidence interval of risk ratio that can be ruled out with 80% probability, for different scenarios with respect to the size of the exposed and comparator groups conservatively assuming N=1000 to be the size of pregabalin-exposed pregnancies. This analysis assumes that the true underlying risk ratio is 1.0 (no association between pregabalin exposure and an endpoint). For example, assuming the background prevalence of major congenital malformations to be 3%, underlying pregabalin-associated RR, and allocation ratio of comparator to pregabalin of 119:1 (corresponding to pregabalin exposure prevalence 0.8%), the analysis will rule out a RR with an upper confidence limit of 1.65845.

Table 5. Maximum upper limits of 95% confidence interval for risk or prevalence ratios depending on the prevalence of selected outcomes representative of prevalence of various study outcomes

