8.7.6. Sensitivity analyses

To reduce the potential bias in the analysis of congenital malformations from not including pregnancies terminated due to known malformations, a sensitivity analysis including these will be conducted in the countries where this information is available (Denmark, Norway and Finland). The sensitivity analyses will be conducted in the following study population/analysis set: pregnancies ending in singleton/multiple live birth, stillbirth, or in therapeutic 2nd trimester induced abortion. The analyses in this population will assess the association of the first-trimester exposure to pregabalin and major congenital malformations, including all the comparators above. Separate descriptive tables will be produced and separate sets of PS will be estimated as appropriate for each contrast in the sensitivity analyses.

In another sensitivity analysis, crude estimates of association for the birth outcomes will be provided defining monotherapy of pregabalin, lamotrigine, and/or duloxetine by absence of other AED, selective serotonin reuptake inhibitors or benzodiazepines. By comparing magnitude and direction of change in the estimates of association obtained in this analysis and those in the main analyses of monotherapy, it will be possible to infer the direction and the amount of any potential unmeasured confounding, thus aiding interpretation of the results (triangulation⁵⁵).

All estimates of association will be reported with Wald 95% confidence intervals (CIs).

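### The termination sensitivity analysis counts Finnish births to 2015 but Finnish terminations only to 2012, so it corrects the selection bias only in part

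*Protocol*

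**What the plan says.** Section 8.3.2 makes Table 2 the place where the population and identification period of each outcome are set. Its sensitivity row reads, for births, "Pregnancies ending in singleton/multiple live birth, stillbirth, 1Jan2005 - 31Dec2015 inclusive and pregnancies ending in therapeutic", with no exception for Finland. The terminations in the same cell run as "induced abortion, 1Jan2005-31Dec2015 inclusive (Denmark, Norway) 31Dec2012 (Finland". Malformations are then followed "until the first birthday (inclusive) through 2016 in Denmark and Norway and 31Dec2016 in Finland", which fits Finnish births up to the end of 2015.

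Section 8.7.6 gives the purpose: "To reduce the potential bias in the analysis of congenital malformations from not including pregnancies terminated due to known malformations". It plans the analysis for all three countries that hold termination records, Finland among them, and sets no dates. The matching objective in Section 7, the study population text in Section 8.2 and the outcome definition in Section 8.3.2.3 also name Finland without a date limit. Section 8.7.1 puts births plus second-trimester terminations in the denominator and does not align their periods. The limitations in Section 8.9 mention unobserved malformations in spontaneous and first-trimester induced abortions, but not this gap. Section 8.2 stresses the nervous system, where "nearly half of the pregnancies affected by nervous system malformations may be terminated".

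**The concern.** The analysis has one job: to show whether leaving out terminated pregnancies distorts the malformation results. In 3 of the 11 Finnish birth years it still leaves them out. Two things follow.

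- **Residual selection bias.** If terminating an affected pregnancy is more or less common among the exposed, that distortion stays in the Finnish births of 2013-2015.
- **A calendar-time artefact.** If exposed pregnancies fall in 2013-2015 more often than comparators do, they lose more of their terminated cases, and the crude ratio drops even when termination does not depend on exposure. The births-only analysis does not have this problem.

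Agreement between this analysis and the primary one could then be read as more reassuring than it is. Finland is also the largest contributor of exposed pregnancies.

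**Working it through.** **1. Dates in the Table 2 row**

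| | Births | Terminations | Malformation follow-up |
|---|---|---|---|
| Denmark, Norway | 2005-2015 | 2005-2015 | through 2016 |
| Finland | 2005-2015 | 2005-2012 | to 31 Dec 2016 |

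Finnish years without terminations: 3/11 = 27%.

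**2. Finland's weight.** Table 4 gives "Pregabalin, first trimester 200 700 200 400" for Denmark, Finland, Norway and Sweden. Finland's share of the three-country total is 700/(200+700+200) = 64%. Against the very large unexposed group, the variance of a log ratio is roughly proportional to 1/(number exposed), so 64% is also about Finland's inverse-variance weight. Against an active comparator the information is about 1/(1/exposed + 1/comparator), assuming equal prevalence:

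- Lamotrigine: Finland 1/(1/700+1/900) = 394; Denmark and Norway each 1/(1/200+1/2000) = 182. Finnish weight 394/758 = 52%.
- Duloxetine: Finland 1/(1/700+1/500) = 292; Denmark and Norway each 1/(1/200+1/400) = 133. Finnish weight 292/558 = 52%.

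**3. Calendar-time artefact (crude, true ratio 1.0).** Let t be the share of affected pregnancies terminated, equal in both groups, and fE and fU the shares of exposed and unexposed pregnancies in 2013-2015. Ignoring small changes in the denominators, the observed ratio is (1 - t·fE)/(1 - t·fU). Take fU = 3/11. The protocol gives no yearly exposure counts, so fE = 0.40-0.50 is an assumption; use rising linearly from zero in 2004 would give (9+10+11)/66 = 45%.

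| t (assumed) | fE = 0.40 | fE = 0.50 |
|---|---|---|
| 0.10, any malformation | 0.960/0.9727 = 0.99 | 0.950/0.9727 = 0.98 |
| 0.20, any malformation | 0.920/0.9455 = 0.97 | 0.900/0.9455 = 0.95 |
| 0.50, nervous system | 0.800/0.8636 = 0.93 | 0.750/0.8636 = 0.87 |

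Only t = 0.50 has support in the text (Section 8.2). With flat use, fE = fU and the ratio is 1.0. Pooled at 64% weight with unbiased Danish and Norwegian estimates, the fE = 0.50 ratios for any malformation become 0.977^0.636 = 0.985 and 0.952^0.636 = 0.97.

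**4. Residual selection bias (true ratio 1.0).** Assume that 3.5% of pregnancies are affected (M), and that 10% of affected exposed and 20% of affected unexposed pregnancies are terminated. With c the share of the period in which terminations are captured, observed prevalence is [M(1-t) + cMt]/[1 - Mt + cMt].

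- No terminations (c = 0): (0.0315/0.9965)/(0.028/0.993) = 1.12.
- Finland as written, 27% of both groups in 2013-2015 (c = 8/11): 0.03408/0.03315 = 1.03. With 60% of both groups there, 1.07.
- Full capture (c = 1): 1.00.

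On these inputs, about a quarter to just over a half of the log bias stays in the Finnish estimate.

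**5. Precision cost of ending Finland at 2012.** Section 8.5 states 1.65845 as the upper limit that can be ruled out at 3% prevalence, 1,000 exposed and 119:1. The formula exp[(1.960+0.842)·√((1-p)/(np) + (1-p)/(119np))] returns 1.65844, so the method is reproduced. Dropping the small comparator term, n = 1,100 gives 1.62. If 27% to 60% of the 700 fall in 2013-2015 (assumed), n falls to 909 or 680 and the limit rises to 1.70 or 1.84.

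**The case against.** A reader might infer that the Finnish estimate keeps the selection bias whole. The documents do not support that: terminations are included for 8 of 11 Finnish years, and Denmark and Norway are fully covered. A reader might also take 0.87-0.93 as the bias of the analysis. That range is crude, Finnish, confined to nervous-system malformations and built on an assumed rise in use. At 0.2-0.4% prevalence, 700 exposed pregnancies yield only 1.4-2.8 such cases, and Table 5 gives a limit of 7.2 at 0.2%, so a shift of that size could not be seen.

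Calendar year of delivery is a propensity-score covariate (Section 8.3.3), separate scores are fitted for this analysis, and balance is checked. Adjusted results should therefore lose much of the artefact in step 3. This stands, but crude estimates are also reported and pooled, and balancing years cannot restore unrecorded terminations: step 4 gives both groups the same calendar distribution and bias remains.

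The inputs to the 64% are soft. The Finnish count is headed "Finland (2005-2014" and so omits 2015, and Norway's 200 is imputed from Denmark, the country with the fewest users, so the true share may be lower. Norway would need more than 700, or 3.5 times its imputed figure, to displace Finland.

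Finally, the 2012 date may be a partly updated entry. The protocol does not say that later Finnish terminations are unavailable. That bears on the remedy, not on the mismatch. Reading 2012 as the end of the whole Finnish window fails, because the birth dates carry no exception and follow-up runs to 2016.

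**Conclusion.** The mismatch is a matter of the printed dates and needs no assumption. As written, Finnish births of 2013-2015 enter without their terminated cases, and no other section aligns or discloses this. The analysis addresses the selection bias in part, not in full.

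The size is less certain. The gap weighs most against the unexposed (about 64% Finnish weight on the Table 4 counts) and less against lamotrigine or duloxetine. The artefact is modest for any malformation and larger for nervous-system malformations, and it vanishes with flat use. Its size rests on assumed termination shares and calendar trends; the residual bias also needs termination to differ by exposure, which the protocol does not quantify. The primary analysis is untouched and country-specific results are reported. This should be fixed, but it does not undermine the study.

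**What to change.** In Table 2 and Section 8.7.6, use one window for Finnish births and terminations in this analysis: both to 31 December 2015 if the termination data can be obtained, otherwise both to 31 December 2012. Beside it, show the births-only estimate re-run on exactly the same country-years (therefore without Sweden), so that only the inclusion of terminations differs.

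Extending terminations to 2015 costs no precision but requires the data. Ending both at 2012 costs some precision in this one analysis, as in step 5. Either way the change is a few words in the protocol plus one extra births-only run, best settled before data extraction.
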